Appendix A

#	CARMELINA trial definitions	Implementation in routine care	References/Rationale	Color coding
	5a-Successful NI with label change		Please see the following Google Drive for further details or any missing information: https://drive.google.com/open?id=1WD618wrywYjEaXzfLTcuk-VCcnb6b-gV	Criteria
	EXPOSURE vs. COMPARISON		ICD-10 codes are not listed in this document because of excel cell size limitations and excessive number of ICD-10 codes. Full ICD-10 code lists will be available in the above Google Drive Folder (link above). ICD-9 to ICD-10 code conversions were completed using a SAS macro that implements forward/ backward mapping based on the CMS ICD-9 to ICD-10 mapping: https://www.ncbi.nlm.nih.gov/pmc/articles/PMC3037733/	Adequate mapping in claims
	Linagliptin 5mg/day vs. placebo	Linagliptin vs. 2nd generation sulfonylureas		Intermediate mapping in claims
	PRIMARY OUTCOME			Poor mapping or cannot be measured in claims
	The primary outcome is the time to the first occurrence of CV death, non-fatal myocardial infarction (MI) or non-fatal stroke—the so-called 3-point major adverse CV events (3P-MACE) composite outcome.	
Measured 1 days after drug initiation in diagnosis position specified below and inpatient care setting:
 
Inpatient mortality/MI/Stroke –
 
For MI Any diagnosis position in inpatient care setting ICD-9 Dx 410.X (acute myocardial infarction) excluding 410.x2 (subsequent episode of care)
 
For stroke Primary diagnosis position in inpatient care setting ICD-9 discharge diagnosis: 430.xx Subarachnoid hemorrhage (SAH) 431.xx Intracerebral hemorrhage (ICH) 433.x1 Occlusion and stenosis of precerebral arteries with cerebral infarction 434.xx (excluding 434.x0) Occlusion and stenosis of cerebral arteries with cerebral infarction 436.x Acute, but ill-defined cerebrovascular events
 
Mortality- See Mortality Sheet.
	
For MI:
 
►PPV 94% in Medicare claims data [Kiyota Y, Schneeweiss S, Glynn RJ, Cannuscio CC, Avorn J, Solomon DH. Accuracy of Medicare claims-based diagnosis of acute myocardial infarction: estimating positive predictive value on the basis of review of hospital records. American heart journal 2004;148:99-104.]
 
►PPV 88.4% in commercially-insured population [Wahl PM, Rodgers K, Schneeweiss S, et al. Validation of claims-based diagnostic and procedure codes for cardiovascular and gastrointestinal serious adverse events in a commercially-insured population. Pharmacoepidemiology and Drug Safety 2010;19:596-603.]
 
For stroke:
 
PPV of 85% or higher for ischemic stroke PPV ranging from 80% to 98% for hemorrhagic stroke
 
 
 
	Can't be measured in claims but not important for the analysis
	INCLUSION CRITERIA			
	1) Documented diagnosis of T2DM before visit 1 (screening).			
	2) Male or female patients who are drug-naïve or pre-treated with any antidiabetic background therapy, excluding treatment with GLP-1 receptor agonists, DPP-4 inhibitors or SGLT-2 inhibitors if ≥ 7 consecutive days.	This is basically everyone except for those with treatment with GLP-1 receptor agonists, DPP-4 inhibitors or SGLT-2 inhibitors if ≥ 7 consecutive days. One of the exclusion criteria below is exclusion based on ≥ 7 consecutive days use of GLP-1 receptor agonists, DPP-4 inhibitors or SGLT-2 inhibitors, so ignoring this inclusion criteria.		
	3) Ssheetle antidiabetic background medication (unchanged daily dose) for at least 8 weeks prior to randomization. If insulin is part of the background therapy, the average daily insulin dose should not have been changed by more than 10% within the 8 weeks prior to randomization compared with the daily insulin dose at randomization.	N/A	-	
	4) HbA1c of ≥ 6.5% and ≤ 10.0% at visit 1 (screening).	N/A	-	
	5) Age ≥ 18 years at visit 1 (screening). For Japan only: Age ≥ 20 years at Visit 1.	Measured 180 days prior to drug initiation Age ≥18 years		

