5.2.2 Specify inclusion/exclusion criteria for cohort entry and define the index date

Inclusion and exclusion criteria were adapted from the trial as closely as possible. Definitions for all inclusion/exclusion are provided in **Appendix A** and are summarized in the flowcharts below.

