Excluded based on Exclusion 11 part 1- life expectancy less than 5 years [using combined comorbidity index as a proxy (365 days)]	-2,263	129,818	-1,125	129,334	-12,200	422,949
Excluded based on Exclusion 11 part 2- History of Malignant Neoplasm (within last 3 years)	-4,153	125,665	-4,128	125,206	-14,241	408,708
Excluded based on Exclusion 12- ACS/unstable angina (≤ 2 months prior)	-374	125,291	-332	124,874	-788	407,920
Excluded based on Exclusion 13- Stroke or TIA (≤ 3 months prior)	-2,292	122,999	-1,981	122,893	-7,081	400,839
Final cohort		122,999		122,893		400,839

* Medicare database includes only patients ≥ 65 years of age with at least one diagnosis for diabetes, heart failure, or stroke.

** Exclusion 8 and Exclusion 10 collapsed for adherence to CMS suppression guidelines.

6. Variables

6.1 Exposure-related variables:

Study drug:

The study exposure of interest is initiation of linagliptin. Initiation will be defined by no use of linagliptin or a comparator in the prior 6 months before treatment initiation (washout period).

Comparator agents:

- Initiators of linagliptin will be compared to initiators of-
 - 2nd generation sulfonylureas

Because linagliptin and comparators are frequently used as second or third line treatments of T2DM, we expect it to be unlikely that linagliptin and comparators are initiated in patients with substantially different baseline risk for proposed outcomes.

6.2 Preliminary covariates:

- Age
- Sex
- Combined Comorbidity Index (CCI), measured over the baseline covariate assessment period, defined as 180 days prior to and including index date

Covariates listed above represent only a small subset of covariates that will ultimately be controlled for in the design and analysis. We use the covariates above only for initial feasibility analyses to judge whether there is likely to be sufficient overlap between treatment groups to proceed with the study. Remaining covariates are defined only after the study has passed the initial feasibility analysis and the initial power assessment and are listed in Table 1 (**Appendix B**). These covariates are based on those used by Patorno et al. (2019).

6.3 Outcome variables and study follow-up:

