6.3.2 Study follow-up

Both as-treated (AT) and intention-to-treat (ITT) analyses will be conducted with treatment defined as the index drug on the day of cohort entry. Because adherence in the real world databases is expected to be much worse than in the trial, the AT analysis is the **primary** analysis, as it targets the relative hazard of outcomes on treatment.

For the AT analyses, the follow-up will start the day after initiation of linagliptin and comparator and will continue until the earliest date of the following events:

- The first occurrence of the outcome of interest, unless otherwise specified for selected outcomes,
- The date of end of continuous registration in the database,
- End of the study period,
- Measured death event occurs,
- Nursing home admission

- Nursing home admissions are considered a censoring event because the data sources utilized typically provide little to no data on a patient, particularly on drug utilization, after admission. We will utilize this as an exclusion reason for cohorts for the same reason.
- The date of drug discontinuation, defined as the date of the last continuous treatment episode of the index drug (linagliptin and comparator) plus a defined grace period (i.e., 30 days after the end of the last prescription's days' supply in main analyses).
- The date of augmentation or switching from an exposure to a comparator or any other agent in the comparator class and vice versa (e.g. switching from glimepiride to glipizide would be a censoring event);
 - A dosage change on the index treatment does not fulfill this criterion
 - An added treatment that is not part of the exposure or comparator group does not fulfill this criterion (e.g. if a linagliptin user adds insulin, he or she does not get censored at the time of insulin augmentation)

For the ITT analyses, the censoring based on the augmentation/switching and treatment discontinuation will be replaced with a maximum allowed follow-up time of 365 days.

7. Initial Feasibility Analysis

Action report links:

Optum: <https://bwh-dope.aetion.com/#/projects/details/702/results/30636/result/0>

Marketscan: <https://bwh-dope.aetion.com/#/projects/details/701/results/30634/result/0>

Medicare: <https://bwh-dope.aetion.com/#/projects/details/703/results/30635/result/0>

Date conducted: rerun on January 28, 2019

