
II. Evidence of impaired renal function with predefined UACR, with or without CV co-morbidities, defined as follows (and/or criteria):
 
 - Impaired renal function (as defined by MDRD formula) with an eGFR: 15-<45 mL/min/1.73 m² at visit 1 (screening) with any UACR. - Impaired renal function (as defined by MDRD formula) with an eGFR ≥ 45-75 mL/min/1.73 m² at visit 1 (screening) with an UACR > 200 mg/g creatinine or 
> 200 μg/min (microgram albumin per minute) or > 200 mg/24 h [milligram albumin per 24 hours] demonstrated in two out of three unrelated spot urine or timed samples in the last 24 months prior to randomization.
	
Measured 180 days prior to drug initiation in any diagnosis position in inpatient or outpatient filters:
 
CKD stage 3 and stage 4
 
585.3x-585.4x
	
CKD stage 1: GFR > 90 CKD stage 2: GFR 60 to 89 CKD stage 3a: GFR 45 to 59 CKD stage 3b: GFR 30 to 44 CKD stage 4: GFR 15 to 29 CKD stage 5: GFR < 15

EXCLUSION CRITERIA		

1) Type 1 diabetes mellitus.
	
Measured 180 days prior to drug initiation in any diagnosis position in inpatient or outpatient care setting:
 
DM type 1-At least 1 inpatient or outpatient ICD-9 Dx code of 250.x1 or 250.x3 or ICD-10 Dx code of E10.x in the 12 months prior to drug initiation. 6-months prior
	

2) Treatment (≥ 7 consecutive days) with GLP-1 receptor agonists, other DPP-4 inhibitors or SGLT-2 inhibitors prior to informed consent. Note: This also includes clinical trials where these antidiabetic drugs have been provided to the patient.
	
Measured 180 days prior to drug initiation as a dispensing for one of the following:
 
Treatment (≥ 7 days) with GLP-1 receptor agonists (lixisenatide, dulaglutide, albiglutide, tiraglutide, exenatide), other DPP-4 inhibitors (alogliptin, sitagliptin, saxagliptin) or SGLT-2 inhibitors (canagliflozin, dapagliflozin, empagliflozin) prior to CED
	

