Concomitant initiation or current use of Insulin; n (%)	1,806 (20.3%)	1,841 (20.7%)	1,393 (16.0%)	1,435 (16.5%)	7,081 (21.3%)	7,195 (21.6%)	10,280 (20.2%)	10,471 (20.6%)	-0.01
Concomitant initiation or current use of Meglitinides; n (%)	118 (1.3%)	129 (1.5%)	191 (2.2%)	187 (2.1%)	821 (2.5%)	860 (2.6%)	1,130 (2.2%)	1,176 (2.3%)	-0.01
Concomitant initiation or current use of Metformin; n (%)	4,016 (45.2%)	3,909 (44.0%)	4,013 (46.0%)	3,970 (45.5%)	13,978 (42.0%)	13,920 (41.8%)	22,007 (43.2%)	21,799 (42.8%)	0.01
Past use of SGLT2i; n (%)	0 (0.0%)	0 (0.0%)	1 (0.0%)	1 (0.0%)	0 (0.0%)	0 (0.0%)	001 (0.0%)	001 (0.0%)	#DIV/0!
Past use of AGIs; n (%)	9 (0.1%)	6 (0.1%)	7 (0.1%)	9 (0.1%)	72 (0.2%)	66 (0.2%)	088 (0.2%)	081 (0.2%)	0.00
Past use of Glitazones; n (%)	198 (2.2%)	193 (2.2%)	317 (3.6%)	311 (3.6%)	742 (2.2%)	734 (2.2%)	1,257 (2.5%)	1,238 (2.4%)	0.01
Past use of Insulin; n (%)	571 (6.4%)	561 (6.3%)	477 (5.5%)	461 (5.3%)	2,189 (6.6%)	2,125 (6.4%)	3,237 (6.4%)	3,147 (6.2%)	0.01
Past use of Meglitinides; n (%)	53 (0.6%)	50 (0.6%)	58 (0.7%)	53 (0.6%)	284 (0.9%)	294 (0.9%)	395 (0.8%)	397 (0.8%)	0.00
Past use of metformin; n (%)	1,000 (11.3%)	998 (11.2%)	1,008 (11.6%)	1,008 (11.6%)	3,747 (11.2%)	3,722 (11.2%)	5,755 (11.3%)	5,728 (11.3%)	0.00
Other Medications									
Use of ACE inhibitors; n (%)	3,677 (41.4%)	3,668 (41.3%)	3,499 (40.1%)	3,486 (40.0%)	12,931 (38.8%)	12,775 (38.3%)	20,107 (39.5%)	19,929 (39.1%)	0.01
Use of ARBs; n (%)	2,818 (31.7%)	2,768 (31.2%)	2,906 (33.3%)	2,848 (32.7%)	11,910 (35.7%)	11,911 (35.7%)	17,634 (34.6%)	17,527 (34.4%)	0.00
Use of Loop Diuretics; n (%)	1,851 (20.8%)	1,824 (20.5%)	1,700 (19.5%)	1,683 (19.3%)	8,927 (26.8%)	8,978 (26.9%)	12,478 (24.5%)	12,485 (24.5%)	0.00
Use of other diuretics; n (%)	441 (5.0%)	433 (4.9%)	413 (4.7%)	439 (5.0%)	1,637 (4.9%)	1,626 (4.9%)	2,491 (4.9%)	2,498 (4.9%)	0.00
Use of nitrates-United; n (%)	753 (8.5%)	769 (8.7%)	730 (8.4%)	744 (8.5%)	3,871 (11.6%)	3,853 (11.6%)	5,354 (10.5%)	5,366 (10.5%)	0.00
Use of other hypertension drugs; n (%)	886 (10.0%)	915 (10.3%)	768 (8.8%)	793 (9.1%)	3,857 (11.6%)	3,850 (11.6%)	5,511 (10.8%)	5,558 (10.9%)	0.00
Use of digoxin; n (%)	202 (2.3%)	219 (2.5%)	280 (3.2%)	272 (3.1%)	1,335 (4.0%)	1,344 (4.0%)	1,817 (3.6%)	1,835 (3.6%)	0.00
Use of Anti-arrhythmics; n (%)	160 (1.8%)	176 (2.0%)	211 (2.4%)	216 (2.5%)	1,078 (3.2%)	1,054 (3.2%)	1,449 (2.8%)	1,446 (2.8%)	0.00

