N antidiabetic drugs at index date									
...mean (sd)	1.76 (0.70)	1.75 (0.68)	1.77 (0.72)	1.77 (0.70)	1.73 (0.70)	1.73 (0.67)	1.74 (0.70)	1.74 (0.68)	0.00
...median [IQR]	2.00 [1.00, 2.00]	2.00 [1.00, 2.00]	2.00 [1.00, 2.00]	2.00 [1.00, 2.00]	2.00 [1.00, 2.00]	2.00 [1.00, 2.00]	2.00 (0.70)	2.00 (0.68)	0.00
number of different/distinct medication prescriptions									
...mean (sd)	11.06 (5.30)	11.07 (5.36)	10.74 (5.13)	10.66 (5.07)	11.45 (5.09)	11.45 (5.01)	11.26 (5.13)	11.25 (5.08)	0.00
...median [IQR]	10.00 [7.00, 14.00]	10.00 [7.00, 14.00]	10.00 [7.00, 13.00]	10.00 [7.00, 14.00]	11.00 [8.00, 14.00]	11.00 [8.00, 14.00]	10.65 (5.13)	10.65 (5.08)	0.00
Number of Hospitalizations									
...mean (sd)	0.13 (0.41)	0.13 (0.41)	0.12 (0.38)	0.12 (0.39)	0.17 (0.48)	0.16 (0.48)	0.15 (0.45)	0.15 (0.45)	0.00
...median [IQR]	0.00 [0.00, 0.00]	0.00 [0.00, 0.00]	0.00 [0.00, 0.00]	0.00 [0.00, 0.00]	0.00 [0.00, 0.00]	0.00 [0.00, 0.00]	0.00 [0.00, 0.00]	0.00 [0.00, 0.00]	0.00
Number of hospital days									
...mean (sd)	0.65 (2.51)	0.67 (2.66)	0.63 (2.74)	0.66 (2.86)	1.03 (3.87)	1.02 (3.97)	0.90 (3.49)	0.90 (3.60)	0.00
...median [IQR]	0.00 [0.00, 0.00]	0.00 [0.00, 0.00]	0.00 [0.00, 0.00]	0.00 [0.00, 0.00]	0.00 [0.00, 0.00]	0.00 [0.00, 0.00]	0.00 [0.00, 0.00]	0.00 [0.00, 0.00]	0.00
Number of Emergency Department (ED) visits									
...mean (sd)	0.50 (1.18)	0.49 (1.40)	0.19 (1.07)	0.19 (1.26)	0.63 (1.43)	0.63 (1.44)	0.53 (1.33)	0.53 (1.40)	0.00
...median [IQR]	0.00 [0.00, 0.00]	0.00 [0.00, 0.00]	0.00 [0.00, 0.00]	0.00 [0.00, 0.00]	0.00 [0.00, 0.00]	0.00 [0.00, 0.00]	0.00 [1.33]	0.00 [1.40)	0.00
Number of Office visits									
...mean (sd)	5.54 (4.50)	5.53 (4.36)	5.93 (5.53)	5.86 (4.31)	6.33 (4.88)	6.36 (4.75)	6.12 (4.93)	6.13 (4.61)	0.00
...median [IQR]	4.00 [2.00, 7.00]	5.00 [3.00, 7.00]	5.00 [3.00, 8.00]	5.00 [3.00, 8.00]	5.00 [3.00, 9.00]	5.00 [3.00, 9.00]	4.83 (4.93)	5.00 (4.61)	-0.04
Number of Endocrinologist visits									
...mean (sd)	0.69 (2.65)	0.80 (2.89)	0.72 (2.77)	0.83 (3.11)	0.94 (3.83)	0.94 (3.69)	0.86 (3.48)	0.90 (3.47)	-0.01
...median [IQR]	0.00 [0.00, 0.00]	0.00 [0.00, 0.00]	0.00 [0.00, 0.00]	0.00 [0.00, 0.00]	0.00 [0.00, 0.00]	0.00 [0.00, 0.00]	0.00 [3.48)	0.00 [3.47)	0.00
Number of internal medicine/family medicine visits									
...mean (sd)	10.20 (14.44)	9.35 (14.18)	7.99 (10.52)	7.84 (10.00)	8.97 (12.50)	8.98 (11.60)	9.02 (12.55)	8.85 (11.84)	0.01

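### The 8-week stable-background criterion is set to N/A, and the matched arms differ in which antidiabetic classes are in use at entry (SGLT2i 0.27% SU vs 2.43% linagliptin); the likely effect on the HR is small

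*Combined protocol and SAP*

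**What the plan says.** Section 5.2.2 states that "Inclusion and exclusion criteria were adapted from the trial as closely as possible". For inclusion criterion 3, Appendix A quotes the trial's requirement of "antidiabetic background medication (unchanged daily dose) for at least 8 weeks prior to randomization" and, for insulin users, that "the average daily insulin dose should not have been changed by more than 10% within the 8 weeks prior to randomization". The implementation column reads N/A and the rationale column holds a dash.

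Elsewhere the plan does use dispensing data for antidiabetic drugs. Exclusion 2 (GLP-1 RA, other DPP-4 inhibitors, SGLT2i) is "Measured 180 days prior to drug initiation as a dispensing for one of the following". Section 6.3.2 dates discontinuation at "30 days after the end of the last prescription's days' supply in main analyses". The six-month washout in Section 6.1 covers linagliptin and the comparator only.

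Table 1 in Appendix B has one row per class that merges starts at entry with current use, for example "Concomitant initiation or current use of Insulin; n". It also has a row for "N antidiabetic drugs at index date". Section 9 calls for a PS built on every listed covariate except laboratory values. Section 13.1 fits the primary Cox model in that matched cohort, with no further adjustment stated.

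**The concern.** A patient who starts a second agent together with the index drug differs from the trial's patient, whose background regimen was settled. The comparison becomes index drug plus another new drug. Because starts and current use share one flag, the PS cannot tell these patients from established users, and no eligibility step removes them.

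If the co-started classes differ by arm after matching, the HR compared with 1.3 and 1.02 partly reflects those other drugs. A second DPP-4 inhibitor in the SU arm would also blur the contrast itself.

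**Working it through.** **Reproducing the plan's power.** Events = 2 x pairs x risk/1,000; power = Φ(ln 1.3 x √events / 2 − 1.96). Optum: 2 x 8,880 x 16.55/1,000 = 293.9 events, power 0.614. MarketScan: 326.0 events, 0.659. Pooled: 2,638.4 events, 0.999999. All match Section 10.

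**SGLT2i at entry, matched cohort (Appendix B, Table 1).** Standardized difference = (p_L − p_S) / √{[p_S(1−p_S) + p_L(1−p_L)]/2}, where S is SU and L is linagliptin.

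| | SU | Linagliptin | Std. diff. |
|---|---|---|---|
| Optum (8,880) | 51 (0.6%) | 267 (3.0%) | 0.18 |
| MarketScan (8,716) | 62 (0.7%) | 559 (6.4%) | 0.31 |
| Medicare (33,319) | 22 (0.1%) | 412 (1.2%) | 0.15 |
| Pooled (50,915) | 135 (0.27%) | 1,238 (2.43%) | 0.19 |

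The pooled value is 0.02166/0.1148 = 0.19. Before matching, the pooled figures were 648/594,152 (0.11%) vs 1,246/51,041 (2.44%), a difference of 0.21, so matching barely moved it. Exclusion 2 removes earlier SGLT2i treatment of 7 days or more, so this row is essentially starts at or just before entry.

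The other merged rows are balanced. Pooled standardized differences for insulin, metformin, glitazones, meglitinides and AGIs are all below 0.01.

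**Untabulated drugs at entry (inferred).** Residual = (mean number of drugs − 1) − (sum of the six class rows)/n. The six are SGLT2i, AGI, glitazone, insulin, meglitinide and metformin.

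| | SU | Linagliptin |
|---|---|---|
| Optum | 0.76 − 6,449/8,880 = 0.034 | 0.75 − 6,595/8,880 = 0.007 |
| MarketScan | 0.77 − 6,224/8,716 = 0.056 | 0.77 − 6,699/8,716 = 0.001 |
| Medicare | 0.73 − 23,790/33,319 = 0.016 | 0.73 − 24,249/33,319 = 0.002 |

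Each mean is printed to two decimals, so each residual carries +/-0.005. Weighted by n, SU has about 300 + 487 + 533 = 1,320 drugs (2.6 per 100 patients) and linagliptin about 65 + 12 + 74 = 151 (0.3 per 100).

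Table 1 does tabulate first-generation SU and pramlintide. Together they account for at most 4 drugs in matched Optum SU patients and 12 in MarketScan, against about 300 and 487. Medicare is suppressed. What remains is mainly GLP-1 RA, other DPP-4 inhibitors or a second SU agent.

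**The two together.** SU: (1,320 + 135)/50,915 = 2.86 per 100. Linagliptin: (151 + 1,238)/50,915 = 2.73 per 100. This agrees with the balanced mean drug count of 1.74 in both arms.

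**Effect on the HR.** Let h be the effect of an SGLT2i on MACE (assumed; not given in the documents). Bias factor = [1 − p_L(1−h)] / [1 − p_S(1−h)].

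| h | Pooled | MarketScan |
|---|---|---|
| 0.5 | 0.989 | 0.971 |
| 0.7 | 0.994 | 0.983 |
| 0.9 | 0.998 | 0.994 |

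If the untabulated SU-arm drugs had the same h, the two imbalances would nearly cancel: at h = 0.5, (1 − 0.0273 x 0.5)/(1 − 0.0286 x 0.5) = 1.001.

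**Power after removing SGLT2i pairs.** At most 135 + 1,238 = 1,373 pairs go. Pooled: 49,542 pairs, 2,567 events on the plan's own pooled risk, power 0.999999. Optum: 8,562 pairs, 0.598. MarketScan: 8,095 pairs, 0.626. Medicare: 32,885 pairs, above 0.9999.

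**The case against.** The strongest reply is that no excess of co-starters in either arm has been shown. That stands. A reader who saw only the SU residual might infer that more SU patients co-start other drugs; adding the SGLT2i row removes that excess. Nor does merging starts with established use explain the observed imbalance: the SGLT2i row holds almost no established users, and the other merged rows are balanced. A reader might suspect different proportions of starts and established use inside the metformin and insulin rows. That is possible, but no figure shows it.

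The residual is also soft. The plan does not define whether the drug count is of classes, agents or components of combination products, and a mean count is not a count of patients. Near-closure in the linagliptin arm argues against a general counting artefact but does not exclude one specific to the SU arm.

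Measured markers of recent instability are balanced in the pooled matched cohort: hospitalization within 30 days 4.0% vs 3.9%, endocrinologist visit within 30 days 11.5% vs 11.7%, hyperglycemia 6.0% vs 6.0%. The trial also admitted drug-naive patients, so not every participant had a background regimen to hold stable. N/A is reasonable for dose, since nothing in the documents shows that a 10% change in insulin dose can be measured. Appendix A's colour key cannot be read in the text, so the absence of any reason for N/A should not be inferred.

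None of this answers the directly tabulated SGLT2i imbalance, above 0.1 in all three databases.

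**Conclusion.** The point holds in a limited form. The class part of criterion 3 could be applied in claims and is not. The matched arms differ in which classes are used at entry: SGLT2i clearly (0.27% vs 2.43%, standardized difference 0.19), and an opposite SU excess of untabulated agents by inference (about 2.6 vs 0.3 per 100 patients). The total of likely co-starts is similar.

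The expected bias is small against the 1.3 margin. From SGLT2i alone it is a pooled factor of 0.989 to 0.998 and a MarketScan factor of 0.971 to 0.994, toward non-inferiority. This assumes a constant drug effect between 0.5 and 0.9.

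A reader might conclude that SGLT2i was left out of the PS, since so large a difference survived 1:1 matching on a score meant to contain it. The tables raise that question; the documents do not settle it. The pooled #VALUE! entries matter because they keep the pooled imbalance out of the balance review, although the counts by database are printed.

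**What to change.** (a) In Table 1, replace #VALUE! with the pooled SGLT2i counts and standardized difference, and make sure that SGLT2i co-initiation is in the PS, as Section 9 requires.

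(b) Add co-initiation of GLP-1 RA, other DPP-4 inhibitors and a second SU agent to Table 1 and the PS. Split each merged row into started in days -56 to 0 and established. State how the number of drugs at index is counted. Then re-match.

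(c) Pre-specify a re-matched sensitivity analysis that excludes patients with a new antidiabetic class, other than the index drug, in days -56 to 0. Leave the dose part of criterion 3 as N/A.

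The data are already in use, so the work is mainly re-running Sections 9 and 10 and repeating their review before the comparative analysis. The sensitivity analysis loses patients. Dropping all SGLT2i pairs leaves pooled power near 1, with Optum about 0.60 (from 0.61) and MarketScan about 0.63 (from 0.66). The loss under the full 56-day rule cannot be computed, because the documents give no counts of recent metformin or insulin starts. The analysis is therefore best read on the pooled estimate.
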